## 5.2 Primary outcomes measure(s)

### ***Clinical evaluation of the OLO (Sight Diagnostics) system:***

- Neutrophil count from OLO (Sight Diagnostics) system and standard laboratory test full blood count (FBC).

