## 5.3 Secondary outcomes measure(s)

### ***Feasibility of recruiting patients and use of the OLO (Sight Diagnostics) system:***

- Proportion of those recruited from those consented and/or approached
- Proportion of recruited participants with a valid (as opposed to an invalid test result) from all recruited participants. A valid result is when the OLO system neutrophil result is  $\pm 0.2 \times 10^9/L$  of the laboratory gold standard result;
- Proportion of recruited participants returning the follow-up survey from all recruited participants;
- Number and type of OLO System (Sight Diagnostics) device flags and error codes raised during device operation for fingerprick versus venous blood sample to assess device accuracy;
- Number of re-takes of finger prick versus venous blood sample to assess device accuracy.
- Number of cases in which a discrepancy between the OLO System and gold standard would change the management of the patient, according to retrospective clinical review.
- Number of patients with valid OLO System test results for:
  - Haemoglobin – (validity  $\pm 0.7$  g/L)
  - Platelets – (validity  $\pm 15 \times 10^9/L$ )
  - Lymphocytes – (validity  $\pm 0.3 \times 10^9/L$ )

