##### **Cohort 2: Pre-SACT (Systemic anti-cancer therapy) ie borderline neutropenia or palbociclib**

- 1) 18 years old or over
- 2) Patients requiring up to date white cell differential or platelet count immediately prior to therapy i.e: Borderline neutropenia confirmed via a routine pre-chemotherapy whole blood neutrophil count, and require a repeat test either on the day of, or before, the next planned chemotherapy appointment or palbociclib therapy

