## **14 Statistical considerations**

### **14.1 Sample size**

#### **14.1.1 WP1 Device cohort study**

##### **Cohorts 1 and 2 combined:**

We will evaluate the concordance between the OLO neutrophil result and the standard of care laboratory result from the same time period, across all patients with a valid output. A valid OLO neutrophil result will be one which produces a test result which is within  $\pm 0.2 \times 10^9/L$  of the standard laboratory result.

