## **15 Analysis**

### **15.1 Quantitative analysis of WP1 device cohort evaluation**

All quantitative analysis will be documented in the SAP [36] prior to implementation of the analysis.

As this is a feasibility study, statistical analysis of study outcomes will be descriptive in nature. Continuous data will be reported as means and standard deviations, or medians and interquartile ranges, as appropriate. Categorical data will be reported as frequencies and proportions. Outcomes will be estimated with their associated 95% confidence intervals.

No formal hypothesis testing will take place.

While subsequent funding is not formally linked to satisfying any specific progression criteria, we propose the following as indicators that a larger study is feasible (NB. Failure to meet one or more of the criteria would indicate that modifications are required, with potentially further feasibility testing, prior to a larger study) as described in Table 7.

**Table 7.** Trial progression criteria

Outcome	Criteria
Recruitment	At least 80% of patients approached to take part provide consent
Intervention adherence	At least 90% of recruited participants receive the OLO test
Intervention fidelity	A valid test result is obtained from at least 90% of recruited participants who receive the OLO test
Survey fidelity	A survey is completed and returned from at least 80% of recruited participants who are given the survey
Data collection	At least 80% of recruited participants have clinical outcome data available for statistical analysis
Staff focus groups	Focus group data indicates that the OLO test is acceptable
Patient focus groups	Focus group data indicates that the OLO test is acceptable

There will be no interim analyses other than TMG review of WP1 SAE's at TMG meetings, Trial Manager review of screening logs through the WP1-3 recruitment phases, and Trial Manager review of data entry after approximately half of the participants have been recruited to WP1.

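### The only agreement outcome for haemoglobin, platelets and lymphocytes is a within-tolerance count, which cannot show the direction of an OLO error or separate bias from scatter

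*Protocol*

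**What the plan says.** Section 5.3 (feasibility outcomes) ends with "Number of patients with valid OLO System test results for" haemoglobin (±0.7 g/L), platelets (±15 x10^9/L) and lymphocytes (±0.3 x10^9/L). The term is explained earlier in the same list for neutrophils: "A valid result is when the OLO system neutrophil result is" within a fixed distance of the laboratory value. The ± limits carry that meaning to the other three analytes.

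Neutrophils are treated more fully. The primary outcome in 5.2 is the neutrophil count itself from both systems, and 14.1.1 adds: "We will evaluate the concordance between the OLO neutrophil result and the standard of care laboratory result from the same time period". Neither provision extends to the other three analytes.

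Section 15.1 gives general reporting rules. For measurements: "Continuous data will be reported as means and standard deviations, or medians and interquartile ranges, as appropriate". For yes/no outcomes: "Categorical data will be reported as frequencies and proportions. Outcomes will be estimated with their associated 95% confidence intervals".

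The Cohort 2 inclusion criterion in 8.1.1 opens with "Patients requiring up to date white cell differential or platelet count immediately prior to therapy", then narrows this, after an i.e., to borderline neutropenia on a neutrophil count, or palbociclib therapy.

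**The concern.** Each Cohort 1 or 2 participant with both results supplies a signed difference, OLO minus laboratory, for each analyte. The defined outcome keeps only whether that difference lies inside the limits. Two things are lost:

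- **Direction.** An over-read and an equal under-read give the same expected count.
- **Type of error.** A steady shift and a wider scatter around zero can give the same count.

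These differ in meaning for a device proposed for pre-treatment checks. A consistent over-read of platelets pushes every reading the same way, whereas scatter around zero does not. Section 14.2 gives a reason to expect one-directional error in at least one analyte: it warns that skin puncture raises white cell numbers near the wound. Finger-prick samples are permitted (12.1.2), and lymphocytes are white cells.

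The point does not depend on where the tolerances are set. Any symmetric tolerance has this effect if only the count is reported.

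**Working it through.** **The plan's own figures.** No precision is stated for these three analytes. The nearest figures are the 95% intervals for the share with a valid result in 14.1.1. The Wilson score interval reproduces them: 43/48 gives 77.8% to 95.5% (Cohort 1), and 22/24 gives 74.2% to 97.7% (Cohort 2).

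**Inputs.**
- Platelet tolerance T = 15 x10^9/L (5.3). In units of T, the results below apply equally to haemoglobin and lymphocytes.
- n = 65, the Synopsis total of valid results. It is a neutrophil figure; up to 72 pairs could be available (72 recruited).
- 90% valid, from 14.1.1 and Table 7. It is also a neutrophil or device figure; no target is given for these analytes.
- The SD of the paired difference is not in the protocol. It is assumed, and a range is shown.

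**Model.** Difference d ~ Normal(b, s). Share valid = Φ((T − b)/s) − Φ((−T − b)/s).

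**Direction.** Replacing b by −b leaves the share unchanged for every s. With s = 5, b = +7.5 and b = −7.5 both give 0.933, or 60.7 of 65 expected valid.

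**Bias against scatter.** With s = 5 and b = 7.5 the share is 0.933. With b = 0 and s = 8.2 it is also 0.933.

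**Sensitivity to a modest bias.**
1. Set 90% valid at zero bias: s = T/1.645 = 0.608T, about 9.1 x10^9/L for platelets.
2. Let b = 0.25T = 3.75 x10^9/L. Share valid = Φ(0.75/0.608) − Φ(−1.25/0.608) = 0.871.
3. From the count: an exact one-sided 2.5% binomial comparison with 90% requires 52 or fewer valid of 65. The probability of that at 87.1% is 0.068. This cut-off has an actual error rate of only 1.1%; moving it to 53 (2.6%) raises 0.068 to 0.124.
4. From the mean paired difference: the two-sided 5% paired t, by the noncentral t with noncentrality (0.25/0.608)√65, gives 0.904.
5. With n = 72 the same steps give 0.073 and 0.931.

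**Other assumptions, n = 65.** The count is compared with the zero-bias share for that SD.

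| SD | Bias | Count | Mean difference |
|---|---|---|---|
| 0.4T | 0.25T | 14.6% | 99.9% |
| 0.5T | 0.25T | 10.0% | 97.8% |
| 0.608T | 0.25T | 6.8% | 90.4% |
| 0.7T | 0.25T | 6.3% | 80.9% |
| 0.608T | 0.33T | 16.6% | 99.1% |

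The protocol plans no hypothesis test, so these figures should be read as the chance that a reported 95% interval would reveal the bias.

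**Precision after the fix.** The half-width of the 95% CI for the mean platelet difference is 1.96s/√n. For s = 3.75, 5 and 7.5 it is 0.9, 1.2 and 1.8 x10^9/L at n = 65, and 1.6, 2.1 and 3.1 at n = 22.

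**The case against.** The strongest reply is that this belongs in the SAP. Section 15.1 sends all quantitative analysis there and provides for means and SDs of continuous data, and section 5.3 nowhere says that only the count will be kept. That stands in part: an SAP could add a mean difference, and nothing forbids it. But the protocol does fix an outcome for these analytes, and an SAP that follows it needs to deliver only the count.

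Four stronger readings are tempting, and the documents do not support them.

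- **That the bias could never be recovered, or that the larger trial would be planned without it.** The trial database holds routine and study blood results (16.2), and the device exports its results (11.1). The loss is in what the plan reports.
- **That platelet count is the main reason for entering Cohort 2.** The criterion is specified as borderline neutropenia or palbociclib, and the primary objective concerns neutropenia.
- **That the tolerances lack any external basis.** Section 5.3 gives no source for them, but the manufacturer's documents cited in the reference list are not available here, so this cannot be checked.
- **That a hidden bias would endanger trial participants.** OLO results are withheld from patient management (11.1, 12.1.2).

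Section 5.3 also counts discrepancies that would change management, and this is not limited to neutrophils. It may expose individual misreadings, but it estimates no bias.

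The illustration is also open to challenge. Nothing in the protocol says that a bias of a quarter of the tolerance matters, and n, the 90% rate and the SDs are borrowed or assumed. This limits the size of the figures. It does not affect the loss of direction, which holds for any SD.

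**Conclusion.** The point holds as an improvement to secondary descriptive outcomes. As defined, the outcome for haemoglobin, platelets and lymphocytes cannot show which way the OLO errs, and it cannot separate bias from imprecision.

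Under normal differences and 90% valid at zero bias, a bias of one quarter of the tolerance has about a 7% chance of being revealed by the count and about 90% by the mean paired difference (about 7% and 93% at n = 72). Over assumed SDs of 0.4 to 0.7 of the tolerance, the gain at n = 65 is about 75 to 88 percentage points.

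The primary outcome is unaffected, and no progression criterion in Table 7 names these three analytes.

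**What to change.** In section 5.3, replace the last bullet with:

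*For haemoglobin, platelets and lymphocytes: mean paired difference (OLO minus laboratory) with 95% CI and 95% limits of agreement, in all Cohort 1 and 2 participants with both results whether or not inside the tolerance, overall and shown separately for finger-prick and venous samples; the number and proportion within tolerance are reported as a supplement.*

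The split by sample type is needed because of the capillary warning in 14.2: a pooled mean could blend two different biases.

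The cost is one outcome bullet and a few table rows. Both values come from the OLO output and the routine full blood count, so no new data or patients are needed. The downside is a few more secondary estimates to report, and the estimates by sample type will be less precise than the overall one.

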### ***Safety:***

- Sepsis-related mortality and morbidity. The number of patients diagnosed with sepsis.

### ***Acceptability of OLO (Sight Diagnostics) system to patients and staff:***

- Acceptability indicators collected via patient focus discussion group (feedback on draft qualitative survey, perceived benefits and disadvantages of the intervention, views around recruitment and/or randomisation in a future UK-wide study design);
- Number of healthcare workers recruited to healthcare worker discussion group meeting (from those invited).

- Number of healthcare workers recruited to healthcare worker discussion group meeting completion (from those screened).
- Acceptability indicators collected via healthcare worker focus group interview (preferred device operator, device placement and blood collection method, perceived benefits and disadvantages of the intervention, potential hurdles to implementation and impact on future UK-wide study).

**Costs:**

- In patients in which the OLO system result could have prevented unnecessary interventions, number of wasted journeys and unnecessary hospital admissions, bed occupancies, and assessments (negative OLO (Sight Diagnostics) system test results);
- Number of patients with increased body temperature, who are otherwise well, with a negative OLO result that would avoid unnecessary assessment of patients in hospitals and cancer centres; Number of detections of low white blood count early to prevent life threatening complications (positive OLO (Sight Diagnostics) System test results and data capturing time of patient in clinical system);
- Number of unnecessary delays in chemotherapy administration;
- Number of unnecessary antibiotic prescriptions;
- Number of inefficient contacts with the NHS and hospital admissions (via screening data of patients not admitted after triage but later found to have neutropenic sepsis);
- Ability of system to provide reassurance and engagement in the management of patients' cancer (indicators collected via patient/carer and healthcare worker focus group interviews).

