Participants in both cohorts will be asked to consent to the provision of a new study blood sample collected via a CE marked finger prick medical device for analysis using the OLO (Sight Diagnostics) System. The results of the OLO (Sight Diagnostics) System will not be used to manage patients participating in either cohort.

**Cohort 3:** Patients attending Velindre Cancer Centre who are currently or have previously been receiving therapy that might cause a low white blood cell count or neutropenic sepsis. These patients will be asked to participate in the survey part of the study only.

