#### **Cohort 1:**

Following current UK NICE guidelines CG151 [3], UK cancer centres instruct patients on chemotherapy to take their temperature if they feel unwell, and to report this by telephone to the centre as soon as possible. These patients will be screened or triaged over the telephone using a set of standard triage questions following the UKONS Acute Oncology Initial Management Guidelines [20; see Appendix 1] and, if considered to have suspected sepsis will be admitted to hospital to undergo assessment. Such patients admitted to VCC will be managed following the local current procedure documented in Neutropenic sepsis: Prevention and Management of suspected and proven neutropenic sepsis at Velindre Cancer Centre [21].

All patients presenting with suspected neutropenic sepsis will have an urgent clinical assessment within 1 hour of admission, including the collection of standard blood samples from a vascular access device for standard peripheral blood cultures and laboratory tests, and administration of appropriate antibiotics.

Telephone triage and follow-up assessment data will be recorded locally at site using the Velindre UKONS Access spreadsheet following standard local procedure. The patient will normally remain in clinic as an inpatient for approximately 1- 4 hours before the standard laboratory tests will be available for initial consultant review.

Once the standard initial assessment process above has been completed, and whilst the patient remains in clinic awaiting their standard results, a member of the treating clinical team (SHO or nurse) who has been delegated the responsibility of recruitment and screening on the ADVANCE Site Staff Delegation Log will review the identifiable personal and clinical information held in the local hospital database(s) and hospital notes to assess if the patient meets the trial eligibility criteria (see Section 8 Participant selection) prior to consenting and registering the patient to the ADVANCE Cohort 1 following an electronic or backup manual registration procedure.

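### Avoided-care and early-detection counts in Section 5.3 need no laboratory confirmation, and the Safety outcome cannot detect neutropenia that OLO misses

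*Protocol*

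**What the plan says.** Section 5.3, Costs, defines three counts through the OLO result:

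- Avoided journeys, admissions, bed occupancies and assessments. The item opens "In patients in which the OLO system result could have prevented unnecessary interventions" and then counts the "number of wasted journeys and unnecessary hospital admissions, bed occupancies, and assessments (negative OLO (Sight Diagnostics) system test results".
- Febrile but otherwise well patients "with a negative OLO result that would avoid unnecessary assessment of patients in hospitals and cancer centres".
- Early detections of a low white cell count, identified by "positive OLO (Sight Diagnostics) System test results and data capturing time of patient in clinical system".

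None of the three mentions the laboratory count, although it is half of the primary outcome (Section 5.2). The items on chemotherapy delays and antibiotic prescriptions name no data source.

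Section 5.3, Safety, reads "Sepsis-related mortality and morbidity. The number of patients diagnosed with sepsis". It is the outcome listed for secondary objective 2 in Section 5.1, the safety of OLO used with telephone triage. Section 6.1.1 states: "The results of the OLO (Sight Diagnostics) System will not be used to manage patients participating in either cohort". Section 12.1.2 repeats this.

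Two other provisions bear on the point. Under feasibility, Section 5.3 counts OLO/laboratory discrepancies that would have changed management on retrospective clinical review. Section 12.1.6 has the treating consultant told the OLO result once the condition has been successfully treated, to learn whether it would have altered care.

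**The concern.** An avoided-care count should credit the device only where its answer was right. These counts are keyed to the test under evaluation and not to the reference test that each Cohort 1 and 2 participant also has. On a literal reading, both kinds of error add to benefit: a false negative enters the avoided-admission count and a false positive enters the early-detection count.

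The Safety outcome does not offset this. Since OLO results never reach care, sepsis deaths, morbidity and diagnoses would be the same whether OLO were perfect or uninformative. Secondary objective 2 cannot be answered by the outcome listed for it.

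At stake is what the study passes on. Section 15.4 uses WP1 data to identify cost drivers and anticipated effect sizes for the larger trial, and Section 12.1.6 says OLO results are intended to manage patients in that trial.

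**Working it through.** **The plan's nearest figure.** The protocol gives no figure for missed neutropenia or avoided admissions. The closest is the Cohort 1 interval for valid results in Section 14.1.1. The Wilson interval is [p + z²/2n ± z√(p(1−p)/n + z²/4n²)] / (1 + z²/n). With p = 43/48 and z = 1.96 it is (0.8958 + 0.0400 ± 0.0952)/1.0800 = 77.8% to 95.5%, as stated. The method is therefore Wilson, and the point does not rest on any error in that calculation.

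**Inputs.** 48 recruited to Cohort 1 (Section 14.1.1). One third neutropenic, from the local audit (Section 4.2.1): 48/3 = 16, leaving 32. Sensitivity (Se) and specificity (Sp) are not in the documents. Se is assumed to be 0.7 to 0.95 and Sp 1.0, and all 48 are assumed to give an OLO reading.

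**Missed patients among OLO negatives.** Missed = 16(1 − Se). OLO negatives = 32·Sp + missed. Chance of at least one miss = 1 − Se¹⁶.

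| Se | Missed | OLO negatives | Share missed | Chance of ≥1 miss |
|---|---|---|---|---|
| 0.95 | 0.8 | 32.8 | 2.4% | 56% |
| 0.90 | 1.6 | 33.6 | 4.8% | 81% |
| 0.80 | 3.2 | 35.2 | 9.1% | 97% |
| 0.70 | 4.8 | 36.8 | 13.0% | >99% |

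Requiring both tests to be negative gives 32 in every row. With Sp = 0.9 the shares are 2.7%, 5.3%, 10.0% and 14.3%.

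**False early detections.** At Se = Sp = 0.9, true positives are 16 × 0.9 = 14.4 and false positives 32 × 0.1 = 3.2. So 3.2/17.6 = 18% of OLO positives would be false.

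**Direction of the avoided-care count.** It equals 32·Sp + 16(1 − Se). With Sp held at 0.9, lowering Se from 0.9 to 0.8 raises it from 28.8 + 1.6 = 30.4 to 28.8 + 3.2 = 32.0. If both fall together from 1.0 to 0.9 to 0.8, it falls from 32.0 to 30.4 to 28.8. The count rises with worsening accuracy only when added false negatives outweigh lost specificity.

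**Precision of a direct safety count.** With no misses in n neutropenic patients, the upper 95% limit is z²/(n + z²) by Wilson and 1 − 0.025^(1/n) exactly. For n = 16 these are 19.4% and 20.6%. For n = 14 (a third of 43 valid results) they are 21.5% and 23.2%.

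**Can the concordance analysis show the misses?** Section 14.1.1 limits concordance to valid results, meaning within ±0.2 ×10⁹/L of the laboratory. At the background level of ≤0.5 ×10⁹/L (Section 4.1), a laboratory value of 0.20 read as 0.60 differs by 0.40, so it leaves the analysis. A value of 0.45 read as 0.60 differs by 0.15, so it stays in as valid although it crosses the level. The larger misses drop out and the smaller ones are not flagged.

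**The case against.** Several replies have force.

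- *A missed patient is not wholly invisible.* A reader might infer that a miss is never counted as harm. The documents do not support that: an OLO-negative, laboratory-neutropenic patient is an obvious candidate for the discrepancy outcome in Section 5.3 and the review in Section 12.1.6. These provisions are incomplete, though. The outcome sits under feasibility, does not separate false negatives from false positives and is not linked to the Costs counts. The review is worded as following successful treatment, which literally leaves out patients who do not recover.
- *The benefit items are not all read from OLO alone.* The first item is limited to unnecessary care, and admitting a laboratory-confirmed neutropenic patient is hard to call unnecessary. Section 4.2.1 also links avoidable admissions to patients without neutropenia. This is a sensible reading, and the mention of negative results may only name the relevant subgroup. But nothing ties *unnecessary* to the laboratory count, and the early-detection item has no such qualifier.
- *A less accurate device need not look better.* The arithmetic above shows that this depends on which error grows.
- *Triage data.* The Costs list also uses "screening data of patients not admitted after triage but later found to have neutropenic sepsis", while Cohort 1 trial screening begins "Once the standard initial assessment process above has been completed, and whilst the patient remains in clinic awaiting their standard results". A reader might infer that non-admitted patients can never appear in the data. That is not established: Sections 3.2 and 9.1.1 also use screening for telephone triage, whose records are kept in the local UKONS spreadsheet.
- *Cross-tabulation belongs in the SAP.* The table itself does. The outcome definitions, however, are fixed in the protocol.
- *Importance.* The outcomes are descriptive, Table 7 does not use them, and the examples in Section 15.4 are bed use, antibiotics and test costs. This limits the severity.

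**Conclusion.** The point holds in a limited form. As worded, the avoided-care and early-detection counts can include OLO errors, and the listed Safety outcome cannot answer the OLO safety objective. The existing discrepancy outcome and review mitigate this without closing the gap.

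The sizes (0.8 to 4.8 missed patients, 2.4% to 13.0% of OLO negatives) are illustrative. They rest on assumed accuracy, on the audit proportion applying to Cohort 1, and on a literal reading of the Costs items. They apply to all 48 tested patients. Among valid results only, a miss at 0.5 is possible only for laboratory values above 0.3 and up to 0.5, so a freely chosen sensitivity would not fit. They do not extend to Cohort 2, for which the protocol gives no numerical definition of borderline.

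This is a moderate matter of outcome definition. It should be corrected before analysis and does not threaten the study.

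**What to change.** In Section 5.3:

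1. Define OLO-positive and OLO-negative at one neutrophil cut-off, chosen by the sponsor, fixed in advance and applied to both tests. The only figure in the documents is the background level of ≤0.5 ×10⁹/L in Section 4.1.
2. Costs: count a journey, admission, bed occupancy or assessment as avoidable only when OLO and laboratory are both negative and the planned clinical review judges it unnecessary.
3. Costs: count an early detection only when the laboratory confirms the low count.
4. Safety: add the number and proportion, with 95% confidence interval, of laboratory-neutropenic patients whom OLO reads as not neutropenic. Use every OLO output, not only those within ±0.2 ×10⁹/L. Keep sepsis events as description.
5. Report the discrepancy outcome by direction of error, and reword Section 12.1.6 so that the review covers all participants whatever their outcome.

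The cost is outcome wording and a 2×2 table from paired counts already collected for the primary outcome. No extra patients or samples are needed. The reported savings may become somewhat smaller, and the miss rate will be imprecise: even no misses in 14 to 16 neutropenic patients leaves an upper limit of about 19% to 23%.
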